3.3 Analysis Populations

The Enrolled set will include all patients who have provided informed consent and have been included into the study data base.

The Full Analysis Set (FAS) will be defined as all patients randomly assigned to a treatment group having completed at least three consecutive study weeks on each treatment period.

The Safety Analysis Set will include all patients having received at least one study treatment tablet after randomisation.

The Per Protocol Analysis Set (PPS) will include all randomised patients meeting the study eligibility criteria and with no major protocol deviations affecting the treatment efficacy (i.e. <10% missing data* in the patient diary and >80% tablet adherence in the drug and placebo period, separately), and also being classified as non-adherent to atorvastatin in the end of the placebo study period by direct blood

STATISTICAL ANALYSIS PLAN for MUScle Side-Effects of atorvastatin in coronary patients (MUSE) – a randomized controlled trial

sample measurement according to Kristiansen et al.¹⁵. Patients being classified as partial adherent or non-adherent to atorvastatin therapy in the end of the atorvastatin study period by direct blood sample measurement (Kristiansen et al.¹⁵) will be excluded from the data analyses concerning blood levels of parent drug and metabolites.

**The percentage of missing data for the core self-reported variables in the diary (i.e. the VAS 0-10 cm likert scale and the 0-10 numeric rating scale) will be reported.*

4 Trial Population

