2.3 Sample size

Sample size calculations are based on our being able to detect a 1 cm difference in the VAS symptom score between the treatment periods on atorvastatin and placebo since the smallest change in VAS symptom score corresponding to ‘a little more’ or ‘a little less’ symptoms was 1.3 cm, with a lower limit of the CI at 1 cm in a previous study by Gallagher et al¹⁴. Gallagher et al. report a standard

STATISTICAL ANALYSIS PLAN for MUScle Side-Effects of atorvastatin in coronary patients (MUSE) – a randomized controlled trial

deviation (SD) of 1.7 for a difference of 1.0 between two VAS symptom scores. Because of the differences in both populations and specific VAS scale between that study in this one, we use SD=2.5 to account for a much larger variation in this study. With n=68, we will have 90% power to detect a difference of 1.0, using a one-sample T test. With n=68, we will also have 80% power to detect a difference of 40% SAMS under statins vs. 15% SAMS under placebo, using the McNemar test for paired probabilities. To account for some missing information due to drop-outs or and protocol deviations, we plan to include 80 patients.

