2.7 Timing of Outcome Assessments

For all clinically planned measures, visits should occur within a window of the scheduled visit. Visits outside visit window is regarded a protocol deviation. The target day and visits window are defined in the protocol as:

STATISTICAL ANALYSIS PLAN for MUScle Side-Effects of atorvastatin in coronary patients (MUSE) – a randomized controlled trial

Visit Label	Target Day	Definition (Day window)
Screening	Day -60 to -1	Prior to Day 0
V1. Baseline	Day 0 (Randomization)	Day 0
V2	56**	Target day \pm 2 days
V3	112**	Target day \pm 2 days
Last study visit*	112**	112

*The last study visit is defined as the visit following the last visit with randomised treatment, and where there is a study end statement.

**According to the protocol, V2 and V3 (last visit) may be scheduled after a treatment period of at least three consecutive study weeks (21 days) in participants with intolerable muscle complaints.

For analysis and tabulation purposes, we define study time points as

Time Point Label	Target Day	Definition (Day window)
TP1. Baseline	Day 0 (Randomisation)	Information up to randomisation
TP2. Week 8	56	Days 1 to 56
TP3. Week 16	112	Days 56 to 112

If more than one visit fall into the same time point interval, information on all visits will be used in the analyses.

3 Statistical Principles

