3.2.2 Protocol Deviations

The following are pre-defined major protocol deviations regarded to affect the efficacy of the intervention:

- Entering the trial when the eligibility criteria should have prevented trial entry
- Discontinuation of intervention before 3 weeks in any treatment period
- Major change in concomitant lipid lowering medication reported by the patients
- Use of prohibited rescue medication
- Received or used other intervention than allocated

Protocol deviations are classified prior to unblinding of treatment. The number (and percentage) of patients with major and minor protocol deviations will be summarised with details of type of deviation provided.

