5.1 General Definitions and Derived Variables

5.1.1 Muscular symptom intensity

Individual mean difference in muscular symptom intensity = Mean muscular symptom intensity (regardless of characteristics and location) reported by the patient the last three weeks during the treatment period on atorvastatin – the last three weeks during the treatment period on placebo. The last consecutive three weeks completed during each treatment period will be used in patients who discontinue due to intolerable muscle symptoms.

Muscular symptom intensity is reported through a 0-10 cm Visual Analogue Scale (VAS) in a patient diary delivered at study start. The patients are asked to also report muscular symptom intensity on a 0-10 Likert scale. Results from the VAS scale will be replaced by the results from the Likert scale in case of missing data on the VAS scale.

VAS scores over the last 3 weeks in each treatment period have been chosen as primary end-point for three reasons: i) to ensure steady state concentrations of atorvastatin; ii) to maximize the likelihood for the symptoms reported to being truly related to the current (and not previous) treatment period; iii) the duration of the treatment period being sufficiently long to produce SAMS (>3 weeks). VAS score has also been chosen as primary outcome in two previous SAMS studies^{16,17}.

5.1.2 The proportion of patients who report muscle symptoms on atorvastatin treatment compared with on placebo (dichotomous SAMS classification)

The proportion of patients who report muscle symptoms on atorvastatin treatment and not on placebo (dichotomous SAMS classification). A 25% intra-individual change in the VAS symptom score has been regarded clinically relevant in a previous validation study of the scale¹⁴. As previously described it has been reported as the smallest change in VAS symptom score corresponding to ‘a little more’ or ‘a little less’ symptoms was 1.3 cm, with a lower limit of the CI at 1.0 cm in a previous study by Gallagher et al¹⁴. Accordingly, confirmed SAMS will be defined as a 25% higher individual VAS score during the treatment period on atorvastatin vs. placebo and ≥ 1.0 cm absolute difference.

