5.2 Primary Outcome Definition

The primary outcome is the difference between the VAS symptom scores for the mean of the last three weeks of the atorvastatin period and the mean of the last three weeks of the placebo period.

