5.3.6 Study safety

- Proportion of patients with new-onset CHD symptoms (e.g. angina, dyspnoea)
- Intolerable muscle symptoms leading to discontinuation from the treatment arm
- Proportion of patients with creatine kinase (CK) > 10 times upper limit of the normal range or alaninaminotransferase (ALT) > 3 times upper limit of the normal range in blood

STATISTICAL ANALYSIS PLAN for MUScle Side-Effects of atorvastatin in coronary patients (MUSE) – a randomized controlled trial

- Proportion of patients with serious adverse events (SAEs) and Suspected Unexpected Serious Adverse Reactions (SUSARS).

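### By default, safety is analysed on a Full Analysis Set that drops patients with under three weeks in either period, and the Safety Analysis Set is assigned to nothing; the primary analysis also lacks a two-directional check on those patients.

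*SAP*

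**What the plan says.** Section 3.3 defines the FAS as "all patients randomly assigned to a treatment group having completed at least three consecutive study weeks on each treatment period". It defines a separate set for safety: "The Safety Analysis Set will include all patients having received at least one study treatment tablet after randomisation". That sentence is the only place where the Safety Analysis Set appears.

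The FAS is the population for the primary analysis (6.3), the denominator for the confirmed-SAMS proportion (6.4.1) and the default for all secondary outcomes (6.4). Safety is one of those secondary outcomes. Section 5.3.6 lists it, and one of its items is "Intolerable muscle symptoms leading to discontinuation from the treatment arm". Sections 6.4.6 and 7.1 say only that results will be descriptive, and section 7 describes how the data are collected. None of the three names a population.

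The primary outcome compares "the mean of the last three weeks of the atorvastatin period and the mean of the last three weeks of the placebo period" (5.2). Patients who stop later for intolerable symptoms are provided for. Their visits "may be scheduled after a treatment period of at least three consecutive study weeks (21 days) in participants with intolerable muscle complaints" (2.7), and section 5.1.1 adds: "The last consecutive three weeks completed during each treatment period will be used in patients who discontinue due to intolerable muscle symptoms".

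Among the major deviations that remove a patient from the per protocol set is "Discontinuation of intervention before 3 weeks in any treatment period" (3.2.2). Section 6.7 offers two sensitivity analyses: the per protocol set, and imputation of no difference between periods where the primary outcome is missing.

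**The concern.** The first issue is an assignment gap with a definite consequence. An analyst who follows the stated default counts stops for intolerable symptoms in a set from which the earliest stops have already been taken out. The set built for the purpose goes unused.

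The second issue is selection in the efficacy analyses. A randomised patient who stops before three weeks in either period, or never starts the second, is outside the FAS. Such stops can depend on symptoms, which are what the trial measures. If early stoppers on atorvastatin would have shown larger differences than completers, the FAS estimate is too close to zero. If early stops fall mainly on placebo, it may be too far from zero. If a patient reacts alike to both treatments, little changes. The planned sensitivity analyses cannot separate these cases.

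**Working it through.** **The plan's own figure.** Section 2.3 uses n = 68, SD 2.5 and a difference of 1.0 cm. The noncentrality is (1.0/2.5) × √68 = 3.298. With 67 df and two-sided 5%, power is 90.2%, which matches the stated 90%. Section 2.3 also allows for loss: "To account for some missing information due to drop-outs or and protocol deviations, we plan to include 80 patients". That leaves 80 − 68 = 12 patients, so the issue is selection and not power.

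**Which set applies to safety.**
- 6.4: FAS, unless noted otherwise.
- 5.3.6: safety is a secondary outcome.
- 6.4.6, 7 and 7.1: nothing noted.
- 7.1 points to 6.4.7, which is muscle symptom location. Sections 6.4.10 and 6.8 contain similar off-by-one references, so this is a numbering slip, but it means that 7.1 does not settle the population either.

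The rule that results is the FAS.

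**Illustration for safety.** Assumed: 68 patients in the FAS, 8 stops for intolerable symptoms in all, and the only patients outside the FAS are those who stop before week 3.

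| Of the 8, stops before week 3 | Safety Analysis Set | FAS |
|---|---|---|
| 4 | 8/72 = 11.1% | 4/68 = 5.9% |
| 2 | 8/70 = 11.4% | 6/68 = 8.8% |
| 0 | 8/68 | 8/68 |

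**Illustration for the primary outcome.** Assumed: 68 FAS patients with mean m and SD 2.5, plus k patients with imputed differences d. A one-sample t test stands in for the covariate-adjusted model.

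- Mean: M = (68m + Σd)/(68 + k)
- Variance: s² = [67 × 2.5² + 68m² + Σd² − (68 + k)M²]/(67 + k)
- Test: t = M/(s/√(68 + k))

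*Zero imputation, m = 0.50.* For k = 4, M = 34/72 = 0.472, s² = (418.75 + 17 − 16.06)/71 = 5.91, the SE is 0.2865 and t = 1.648.

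| k | Mean (cm) | 95% CI | p |
|---|---|---|---|
| 0 | 0.500 | −0.105 to 1.105 | 0.104 |
| 4 | 0.472 | −0.099 to 1.044 | 0.104 |
| 8 | 0.447 | −0.094 to 0.988 | 0.104 |
| 12 | 0.425 | −0.089 to 0.939 | 0.104 |

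The estimate and the interval shrink toward zero while p does not move. From k = 8 the upper limit lies below the 1 cm design difference.

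*Other values, common to all added patients.* At m = 0.50, k = 4 and d = +1.86: M = (34 + 7.44)/72 = 0.576, the SE is 0.2886, t = 1.994 and p = 0.0499.

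| FAS mean | p, FAS alone | Common difference that changes significance |
|---|---|---|
| 0.50 | 0.104 | p < 0.05 with four at about +1.86 cm or two at about +4.2 cm |
| 0.70 | 0.024 | significance lost with four at about −1.43 cm, two at about −2.70 cm or one at about −4.95 cm |

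Unequal values with a similar total act alike. At m = 0.50, +6 and +3 cm give p = 0.049, and +3, +3, +1 and +1 cm give p = 0.048.

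**Illustration for confirmed SAMS.** Assumed 20/68 = 29.4% (Wilson 95% CI 19.9 to 41.1). Counting none or all of the excluded patients as confirmed gives:
- k = 4: 20/72 = 27.8% to 24/72 = 33.3%.
- k = 12, the whole allowance and so an outer limit: 20/80 = 25.0% to 32/80 = 40.0%.

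**The case against.** Much can be said for the plan. A paired three-week outcome cannot be computed without three weeks in each period, so some restriction is unavoidable, and stops at 21 days or later are kept. Exclusions from the primary analysis and discontinuations are to be shown with reasons in the flow diagram (4.1), and major deviations are to be summarised by type (3.2.2). Section 6.7 has no FAS restriction, and a patient without a three-week mean is missing the primary outcome in plain words. The name of the Safety Analysis Set also suggests its use.

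Most of this stands, and it limits the second point. It does not remove the first: a name is not an assignment, and the only explicit rule says FAS. Nor does it supply the missing check. Counts with reasons do not show what the excluded patients do to the estimate. The per protocol analysis applies the same exclusion. A zero difference is one scenario even if 6.7 covers everyone; 6.6 mentions only patients missing both scales, so the coverage is open to two readings.

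A reader might go further and infer that the primary estimate is biased toward zero, or that early stops would go unreported. The SAP supports neither. It gives no rate of early stops and no symptom values for them, and it reports the exclusions elsewhere.

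**Conclusion.** The safety point holds on the text alone. The stated default sends 5.3.6 to a set that omits the earliest discontinuations, and the Safety Analysis Set has no role. How much this alters a reported proportion depends on how many stops come before week 3: nothing if there are none, and roughly a halving in the assumed case of 4 of 8.

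The efficacy point is a cheap improvement and not a demonstrated bias. The FAS is in effect a three-week completer set, and any bias has unknown size and direction and may be small. What can be said is that zero imputation leaves p essentially unchanged, pulls the estimate toward zero and so cannot show bias toward zero. In a borderline result a few excluded patients, or even one with a large difference, could change significance. The efficacy figures rest on assumed FAS means, an assumed number of excluded patients, the plan's n = 68 and SD 2.5, and a simpler test than the planned model; the confirmed-SAMS count is also assumed.

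**What to change.** 1. In 6.4.6 and 7.1, state that all safety outcomes, including 5.3.6, are analysed on the Safety Analysis Set by the treatment received in the period, with washout events listed separately. Correct the reference in 7.1 to 6.4.6.
2. Leave the primary analysis unchanged. In 6.7, state that the zero imputation covers all randomised patients without a primary outcome, including those outside the FAS.
3. Add a pre-specified tipping-point analysis using the covariate-adjusted model of 6.3. Vary the imputed difference in both directions within the VAS limits (−10 to +10 cm), separately for patients who stopped on atorvastatin, patients who stopped on placebo, and all others without an outcome (for example those who never started period 2 or took no tablet).
4. Report confirmed SAMS also over all randomised patients, with bounds that count none and all of the excluded as confirmed.

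The cost is SAP wording and a little programming, with no new data. The downside is a wider range of reported results, and the tipping-point grid has to be read as a range, since no single cell is an estimate.

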1.2.2 Secondary Objectives

The secondary objectives of this study are:

- To determine the proportion of patients who report muscle symptoms on atorvastatin treatment compared with on placebo (dichotomous SAMS classification)
- To determine the correlation between muscular symptom intensity and blood concentrations of parent drug and metabolites of atorvastatin in patients with confirmed SAMS*
- To determine the diagnostic properties of blood concentrations of parent drug and metabolites of atorvastatin for classification of confirmed SAMS*
- To determine adherence to the study medication (i.e. atorvastatin and placebo) during the treatment periods
- To compare blood concentrations of parent drug and the metabolites of atorvastatin between patients with failing placebo-test (i.e. non-SAMS)* for connecting SAMS to atorvastatin and the control group without muscle symptoms
- To describe study safety

**Confirmed SAMS is defined as at least $\geq 25\%$ higher mean muscle symptom intensity (measured on a 0-10 cm Visual Analogue Scale [VAS]) and a 1cm difference during the last 3 weeks on treatment with atorvastatin compared to placebo. All other patients in the are defined as non-SAMS.*

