3.2 Adherence and Protocol Deviations

3.2.1 Adherence to Allocated Treatment

Adherence to study treatment is based on both **indirect** and **direct** methods:

Indirect method:

Adherence for each patient is based on pill counts in returned containers. It is defined as:

STATISTICAL ANALYSIS PLAN for MUScle Side-Effects of atorvastatin in coronary patients (MUSE) – a randomized controlled trial

% adherence = proportion of days covered (PDC) = $(1 - \text{number of remaining pills}/\text{number of pills delivered to patient}) \times 100\%$

Low adherence = PDC <80% in at least one of the two treatment periods.

Mean (SD) PDC and the proportion of patients with PDC <80% will be presented for all patients and stratified for (i) treatment order allocation and (ii) patients with confirmed SAMS vs. non-SAMS.

Direct method:

Adherence to study treatment will also be determined directly in blood at the end of each treatment period with our liquid chromatography–tandem mass spectrometry method¹² classified according to the algorithm published by Kristiansen et al.¹⁵.

Adherence = patients being classified as non-adherent to atorvastatin in the end of the placebo study period *and* adherent to atorvastatin therapy in the end of the atorvastatin study period according to Kristiansen et al.¹⁵.

Low adherence = all patients not classified as adherent as defined above.

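### The per protocol set uses the atorvastatin assay at the end of placebo only, so patients the assay classifies as non-adherent on atorvastatin can stay in and dilute the per-protocol VAS difference

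*SAP*

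**What the plan says.** SAP section 3.2.1 sets up two measures of adherence. The indirect one is the pill count. The direct one is a blood assay at the end of each treatment period, and it is a joint condition: the patient must be classified as non-adherent to atorvastatin at the end of placebo and "adherent to atorvastatin therapy in the end of the atorvastatin study period". The rest are covered by one line: "Low adherence = all patients not classified as adherent as defined above".

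Section 3.3 defines the PPS. Besides eligibility, absence of major deviations and limits on missing diary data, it asks for ">80% tablet adherence in the drug and placebo period, separately". It then adds one assay condition, for the placebo period: "and also being classified as non-adherent to atorvastatin in the end of the placebo study period by direct blood" sample measurement. The next sentence turns to patients whom the assay classifies as partially adherent or non-adherent at the end of the atorvastatin period. They "will be excluded from the data analyses concerning blood levels of parent drug and metabolites", and no other exclusion is stated for them.

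The PPS is used for a secondary analysis of the primary outcome (6.3), listed again as a sensitivity analysis (6.7). The primary analysis is on the FAS.

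**The concern.** A per-protocol analysis is meant to estimate the difference between the periods when the allocated treatment was actually taken. For that, atorvastatin present during placebo and atorvastatin absent during the active period both matter. The plan screens for the first by assay. For the second it relies on returned tablets, which cannot show whether a missing tablet was swallowed.

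A patient who discards tablets, has no atorvastatin in blood at the end of either period and reports the same symptoms in both is low-adherent under 3.2.1 but per protocol under 3.3. That patient contributes a difference of zero.

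What is at stake is how the PPS result can be read. If it is close to zero, the natural conclusion is that symptoms do not depend on the drug even when it is taken. As now defined, the set does not fully support that conclusion, because some of its members may not have taken the drug. The SAP gives no reason for the asymmetry.

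**Working it through.** **Which rules apply to a patient who fails the assay in the atorvastatin period**

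| Rule | Section | Removes the patient from the per-protocol VAS analysis? |
|---|---|---|
| Assay at end of placebo | 3.3 | No, this patient passes it |
| Pill count above 80% in each period | 3.3 | Only if the returned tablets show it |
| Assay at end of atorvastatin | 3.3 | No, exclusion is from blood-level analyses only |
| Direct-method adherence | 3.2.1 | No, it labels the patient low-adherent but 3.3 does not call on it |
| Major deviation: "Received or used other intervention than allocated" | 3.2.2 | Not clearly, since it names no assay criterion |

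The last row could be stretched to cover non-takers. The explicit sentence in 3.3 on assay failures in the atorvastatin period speaks against that reading.

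**The plan's own figure.** Inputs from SAP 2.3 and 2.4.2: difference 1.0 cm, SD of the within-patient difference 2.5 cm, two-sided 5%, one-sample t test. With noncentrality (1.0/2.5)√n, the smallest n with at least 90% power is 68, and power at n = 68 is 90.2%. The stated n = 68 is reproduced.

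**Dilution.** Let f be the share of the PPS with no atorvastatin exposure and a true difference of zero. Let the others have the planning difference of 1.0 cm.

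- Expected PPS difference = 1.0 × (1 − f)
- SD of the mixture = √(2.5² + f(1 − f) × 1.0²)

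The SAP gives no value for f, so a range is shown. A PPS of 68 patients is also an assumption, borrowed from 2.3. In the right-hand columns the unexposed are removed, so n = 68(1 − f), rounded, with the difference back at 1.0 cm and SD 2.5.

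| f | Difference, kept | SD, kept | Power, kept (n = 68) | n, excluded | Power, excluded |
|---|---|---|---|---|---|
| 5% | 0.95 cm | 2.509 | 87% | 65 | 89% |
| 10% | 0.90 cm | 2.518 | 83% | 61 | 87% |
| 20% | 0.80 cm | 2.532 | 73% | 54 | 82% |

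**Partial adherers.** If the affected patients keep a fraction r of the effect, the expected difference is 1.0 × (1 − f(1 − r)). With f = 10% and r = 0.5 (assumed for illustration) it is 1 − 0.10 × 0.5 = 0.95 cm rather than 0.90 cm. If atorvastatin has no true effect there is nothing to dilute.

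**The case against.** The strongest objection is that the two assay conditions are not mirror images. Drug in blood at the end of placebo is contamination. Low drug at the end of atorvastatin may be a consequence of the outcome: a patient with symptoms stops or skips tablets, has a genuine positive VAS difference, and then has a poor sample. Section 2.7 allows visits to be brought forward for intolerable complaints, and 5.1.1 then uses the last three completed weeks. Excluding such patients would itself pull the PPS toward zero.

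This is right in principle but limited in reach. The pill count in 3.2.1 is computed on tablets delivered. Assume one tablet a day and a full supply for the 7-week period (49 tablets). A patient who stops after 21 days has a count of 1 − 28/49 = 43% and is already outside the PPS. Passing 80% needs more than 0.8 × 49 = 39.2 tablets, so only someone who stops in about the last nine days can pass. Late stoppers and partial adherers remain. For them the point stands, and it is a reason to report both versions rather than replace one with the other.

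It can also be said that 3.2.1 defines a descriptively reported outcome (5.3.4, 6.4.4) and nowhere claims to define the PPS. A reader might infer a flat contradiction between 3.2.1 and 3.3. The text does not support that, because 3.3 states its narrower rule openly. What remains is an unexplained mismatch with a predictable direction of bias.

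Finally, the affected group may be small. These patients must pass the pill count, diary and deviation rules and still fail the assay, and the SAP describes close monitoring (6.6) and weekly telephone contact (section 7). That is fair. Nothing in the SAP supports any particular f, including the 20% row.

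**Conclusion.** The point holds for the per-protocol analysis of the primary outcome. Section 3.3 uses half of the direct-adherence definition, so a patient classified as low-adherent by the trial's own assay can remain in the set. Given a true effect, each such unexposed patient moves the PPS difference toward zero: by 0.05 cm at f = 5% and 0.10 cm at f = 10% from the planning value of 1.0 cm. These sizes rest on an assumed f, a zero difference in non-takers and a true effect of 1.0 cm.

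The reach is limited to one secondary or sensitivity analysis. The FAS analysis, the decision rule and n = 68 do not depend on it.

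A reader might infer that the rule also lowers the confirmed-SAMS proportion, since under 1.2.2 "All other patients in the are defined as non-SAMS" and an unexposed patient would fall there. That does not follow. Section 6.4.1 divides by the FAS, which contains such patients whatever the PPS rule says. Nor can the 40% in 2.3 be scaled down to size such an effect: it is the assumed frequency of SAMS under statins, set against 15% under placebo, and not the proportion with confirmed SAMS.

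**What to change.** In 3.3 and 6.7, add an analysis of the primary outcome on a PPS that meets the full direct-method definition of 3.2.1: non-adherent to atorvastatin by assay at the end of placebo and adherent by assay at the end of the atorvastatin period. Report it beside the PPS as now defined, with the number of patients who differ between the two sets. State explicitly whether partially adherent patients are in or out of the stricter set.

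The cost is wording in two sections and one extra model run, since the assay is already planned at the end of each period. The stricter set will be somewhat smaller. It also carries some selection, because a poor end-of-period sample can follow from stopping late because of symptoms. With both results side by side, a reader can see how far the conclusion depends on the choice.
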